Cut down, Annoyed, Guilty, and Eye-opener (CAGE).....	19
PTSD Checklist – short version (PCL-5).....	19
Data and Safety Monitoring (DSM) Plan.....	20
Monitoring Entity, Roles and Responsibilities	20
Roles of the SMC	20
Responsibilities of the SMC.....	20
Meetings of the SMC	21
Procedures for monitoring study safety, minimizing research-associated risk and protecting confidentiality of participant data	21
Procedures for Identifying, Reviewing, and Reporting Unanticipated Events	22
Compliance across Sites.....	23
Study Completion and Closeout Procedures	25

PRÉCIS

Short Title: Preoperative Pain and Rehab Education (PrePARE)

Objectives

[figure not shown]
Using a multi-site, double-blind, two-arm, parallel, randomized controlled trial with Veterans at-risk for PPSP post-TKA, the following aims will be addressed:

1. Primary Aim: To examine the superior efficacy of ACT versus Attention Control (AC) on postoperative pain intensity and functioning in at-risk Veterans undergoing TKA. Changes in pain intensity and functioning from baseline to 6 weeks, 3 months and 6 months post-TKA will be compared. Level of pain intensity will be measured using the BPI Pain Severity Subscale and level of functioning will be measured using the KOOS Activities of Daily Living and Quality Of Life Subscales.
2. Secondary Aims: A) To examine the superior efficacy of ACT versus AC on the severity of anxiety and depressive symptoms and improvements in coping skills. Changes from baseline to 6 weeks, 3 months and 6 months post-TKA will be compared. Anxiety and depressive symptoms will be measured with the Depression, Anxiety and Stress Scale (DASS-21). Coping skills (i.e. Pain Acceptance and Engagement in Values-Based Behavior) will be measured with the Chronic Pain Acceptance Questionnaire and the Chronic Pain Values Inventory. B) To evaluate whether decreases in distress-based symptoms and increases in coping skills mediate changes in pain and functioning at 6 months in Veterans receiving ACT. Changes in anxiety symptoms, depressive symptoms, pain acceptance and engagement in values-based behavior from baseline to 6 weeks and 3 months will be used as potential mediators for changes in pain and functioning at 6 months.

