3. Exploratory Aim: Describe the pharmacological and non-pharmacological strategies Veterans are using to manage pain and their perceived helpfulness. This will provide insights into the effects of the current opioid restrictions on pain management strategies. These strategies & their perceived helpfulness will be assessed using the Pain Management Strategies Survey at baseline, 6 weeks, 3, and 6 months.

Study Design

The proposed study is a multi-site, double-blind, two-arm, parallel, randomized controlled trial. At-risk Veterans will be randomly assigned to one of two groups: 1) Acceptance and Commitment Therapy (ACT); or 2) Attention Control (AC). Primary and secondary outcomes will be measured at 6 weeks, 3 and 6 months but 6 months will be the primary outcome endpoint for determining mediator effects. Data collected at postoperative week 1 will be used as potential moderators of treatment response.

Schema

Inclusion and Exclusion Criteria

The target study population is veterans undergoing unilateral total knee arthroplasty (TKA) who are at-risk for persistent postsurgical pain (i.e. report moderate to severe preoperative pain in the presence of anxiety and/or depression OR report severe pain and absent anxious and depressive symptoms). A total of 430 participants (215 per group) will be recruited to achieve 150 subjects per group.

Inclusion Criteria

Participants must meet all the following inclusion criteria to participate in this study:

- Veteran;
- 18 years old or older;
- Having unilateral total knee arthroplasty (TKA);
- At risk for pain, anxiety, depression and/or stress, or pain catastrophizing defined as 1, 2, 3 or 4 (below):
 1. Worst pain greater than or equal to 7 on BPI (severe pain)
 2. Worst pain 3-6 (moderate to severe pain) on BPI AND anxiety symptoms (anxiety score greater than or equal to 6 on the DASS 21 or DASS stress score greater than or equal to 10)
 3. Worst pain 3-6 (moderate to severe pain) on BPI AND depressive symptoms (depression score greater than or equal to 7 on the DASS 21)
 4. Worst pain 3-6 (moderate to severe pain) on BPI AND PCS score greater than or equal to 20

Exclusion Criteria

All candidates meeting any of the exclusion criteria will be excluded from study participation.

Exclusion criteria are:

- Inability to complete study forms because of language/literacy barrier;
- Bipolar or psychotic disorder;
- History of brain injury (moderate to severe TBI, other severe injury);

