For variables in the primary aim (pain severity and functioning), efficacy of ACT compared to AC at 6 weeks, 3 months and 6 months will be tested using linear mixed model analysis for repeated measures. The fixed effect in the model will include intervention group, time, and intervention*time interaction effect. The model will also include site, workshop (cluster) within intervention, and subject as random effects. Test of mean contrast will be used to compare between treatment group means and mean change from baseline to 6 weeks, 3 and 6-months post-TKA between ACT and AC. P-values will be adjusted using Bonferroni's method to account for the number of tests performed. The efficacy of ACT versus AC will be expressed as the group mean difference with a 95% confidence interval (CI), using the SAS STAT (14.1) MIXED procedure.

For the secondary aim (A), efficacy of ACT compared to AC on anxiety symptoms, depressive symptoms, pain acceptance, and engagement in values-based behavior will be compared using linear mixed model for repeated measures. Intervention group mean differences will be estimated and tested as described in the analysis for the Aim1 variables.

For the primary and secondary aim analyses, it is expected that randomization will lessen the need for covariate or moderator adjusted analyses. However, if any demographic, baseline, time from workshop to surgery, or perioperative variables (i.e. perioperative anesthesia/analgesic, postoperative complications, postop day 1 pain and function, etc.) are found to differ between intervention groups, the model will be expanded to include these variables as covariates or effect moderators to estimate and test intervention group mean differences, or odds ratio, controlling for these variables.

In addition to the analyses described above for the primary & secondary outcome measures, similar linear mixed model analyses that include all randomized subjects will be performed. This secondary analysis will include surgery status in the model to contrast the impact of the intervention on those with and without surgery.

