For the secondary aim (B), mediation analysis will explore the causal pathway between intervention (ACT or AC) and change in pain intensity and functioning from baseline to 6 months with decreases in anxiety and depressive symptoms, and increases in acceptance-based coping and engagement in values-based behaviors from baseline to 6 weeks, and baseline to 3 months as mediators. With the independent variable X (intervention) randomized to workshops (clusters), and the mediator variables M (decreases in anxiety and depressive symptoms and increases in acceptance-based coping and engagement in values-based behaviors), and the dependent variable Y (changes in pain & function) measured at the subject level within clusters, we have a two-level hierarchy with a 2-1-1 design. For this multilevel design, multilevel structural equation modeling (MSEM) will be used to estimate and test the direct and indirect effects to assess multilevel mediation as described by Preacher, Zyphur, and Zhang¹⁰⁵ using SEM in Stata.

In the case of subject drop-out, reasons for subject drop-out will be recorded and compared between treatment groups. Subject characteristics and outcome measures collected prior to drop-out for those that drop out post-surgery will be compared to those that complete the study. In the presence of missing data, under the assumption of missing at random (MAR), linear mixed model analysis which can handle incompletely observed subjects and uses a likelihood estimation method will provide correct likelihoods and lead to valid estimates.¹⁰⁶ Similarly, the use of the weighted GEE method is able to handle missing responses caused by dropouts in a longitudinal study.¹⁰⁷ However, since the data under analysis cannot distinguish if data is MAR or it is missing not at random (MNAR), sensitivity analysis will also be performed using pattern mixture models. Multiple imputation will be used for sensitivity analysis by imputing from a non-random pattern mixture model.¹⁰⁸

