Participants will be allowed to take breaks and lunch will be provided (at in-person workshops only). Participants will be sent an invitation approximately 2 weeks before their scheduled workshop, a reminder letter 1 week before the workshop and, if they have consented to participate in the Department of Veterans Affairs' Annie mobile Short Message Service (SMS) text messaging, a short text message reminding them of the workshop. They will also receive a reminder call and message one day before the workshop. If participating in an online Zoom workshop, the participant will be sent instructions for using Zoom and a link to join the workshop via their own computer/tablet or they will be sent an iPad via registered mail with the link bookmarked. A research team member will also call the participant the day before to review the instructions for connecting to the virtual workshop. If a participant fails to attend their scheduled workshop, they will be contacted to reschedule. If they repeatedly fail to attend a workshop and do not respond to attempts to reschedule, a letter will be sent requesting they contact the study.

ACT

The ACT workshop will cover the following topics 1) Acceptance and Mindfulness Training emphasizing new ways of managing troubling thoughts, feelings, and physical sensations (e.g., learning how to recognize, and develop cognitive distance from, unhelpful thoughts such as "I can't take this pain anymore" or "This is unfair") and learning how to willingly face experiences that cannot be changed; and 2) Behavioral Change Training involving a) teaching patients how to recognize ineffective patterns of behavior and habits, b) exploring and setting life goals and goals related to mental and physical health, and c) promoting effective and committed actions to achieve these goals despite the urge to do otherwise. Participants in the ACT workshop will receive two manuals and a deck of therapy cards. At the end of the ACT workshops, ACT participants will be asked to document a goal that will be reviewed at the booster session.

AC

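### Aim B asks about mediation in Veterans given ACT, but the planned model has no arm-specific mediator-to-outcome slope and leaves the equal-slope assumption it needs unstated and unchecked

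*Combined protocol and SAP*

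**What the plan says.** Under Objectives in the Précis, Secondary Aim B asks whether falls in distress and gains in coping "mediate changes in pain and functioning at 6 months in Veterans receiving ACT".

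The Data Analysis section of the Précis turns this into a model. It says that "mediation analysis will explore the causal pathway between intervention (ACT or AC) and change in pain intensity and functioning from baseline to 6 months", with changes in the mediators to 6 weeks and to 3 months. Intervention is X, assigned to workshops. Mediators M and outcome Y are measured on subjects, and "we have a two-level hierarchy with a 2-1-1 design". It continues: "multilevel structural equation modeling (MSEM) will be used to estimate and test the direct and indirect effects to assess multilevel mediation".

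No intervention-by-mediator term, multi-group model or ACT-arm estimate is named. Two other sentences mention moderators, and neither fills the gap:

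- Under Study Design: "Data collected at postoperative week 1 will be used as potential moderators of treatment response". This concerns week 1 data only.
- In the Data Analysis paragraph on covariates: "the model will be expanded to include these variables as covariates or effect moderators". This concerns demographic, baseline, timing and perioperative variables that turn out to differ between groups.

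**The concern.** The aim is worded for people who received ACT; the analysis is a contrast of ACT with AC. For a mediation analysis the two can differ. The pathway under ACT is the effect of ACT on the mediator times the mediator-to-outcome slope among ACT recipients. A model without an arm-specific slope uses a slope to which both arms contribute.

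The protocol's description of ACT gives a reason to ask whether the slopes are equal. The workshop teaches cognitive distance from unhelpful thoughts and aims at "promoting effective and committed actions to achieve these goals despite the urge to do otherwise". Training of that kind could weaken the link from distress to function in the ACT arm, or strengthen the link from acceptance to function. That is a rationale, not evidence.

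At stake is the mechanism conclusion. If the link is weak under ACT and strong under AC, a pathway could be credited to ACT that rests on control-arm data. If the reverse holds, the ACT pathway is understated.

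**Working it through.** **1. Design size.** The documents give no power, path size or slope for the mediation analysis, so the trial's dimensions come from the Sample Size section: difference 8, SD 18, alpha 0.0167 (two-sided assumed), power 0.80, 6 per workshop, ICC 0.06, 150 per arm.

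- Individual-level n per arm = 2 × (2.393 + 0.842)² × (18/8)² ≈ 106. The design effect is 1 + (6 − 1) × 0.06 = 1.3, and 106 × 1.3 = 137.8.
- A workshop-level t-test (degrees of freedom = workshops minus 2) gives power 0.791 with 24 workshops per arm (144 Veterans) and 0.811 with 25 (150 Veterans). This reproduces 150 per arm.
- Enrolment: 300/(1 − 0.30) = 428.6, in line with 430.

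The check therefore uses 25 workshops of 6 per arm.

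**2. What a shared slope estimates.** Let a be the effect of intervention on the mediator, b1 and b0 the slopes in ACT and AC, and v1 and v0 the within-arm mediator variances. With equal arms:

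shared slope ≈ (v1·b1 + v0·b0)/(v1 + v0), which is (b1 + b0)/2 when v1 = v0.

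The ACT-arm indirect effect is a·b1. With equal variances, the error from using the shared slope is a·(b0 − b1)/2. At a = 0.5 SD (assumed):

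- b1 = 0, b0 = 0.5: 0.5 × 0.25 = 0.125 against 0.
- b1 = 0.2, b0 = 0.5: 0.5 × 0.35 = 0.175 against 0.100, 75% too large.
- b1 = 0.5, b0 = 0.2: 0.175 against 0.250, 30% too small.
- b1 = b0 = 0.35: 0.175 against 0.175, no error.

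Unequal variances shift the weights. With b1 = 0, b0 = 0.4 and the mediator SD in ACT 0.7 times that in AC, the shared slope is 0.4/(1 + 0.49) = 0.268 (simulated 0.269).

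**3. Simulation.** ICC 0.06, a = 0.5 SD, Monte Carlo 95% intervals for the product. Two stand-ins were used. One is a single-level regression with workshop-robust standard errors. The other is a regression on workshop means, because X varies only between workshops and the indirect effect in a 2-1-1 model runs through the between-workshop path. Ranges are across repeat runs.

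| Slopes ACT / AC | ACT value | Pooled estimate (single-level) | Coverage of ACT value, single-level | Coverage, workshop-level |
|---|---|---|---|---|
| 0 / 0.5 | 0 | 0.124–0.125 | 7–9% | 62–64% |
| 0.2 / 0.5 | 0.100 | 0.175 | 70–75% | 90% |
| 0.5 / 0.2 | 0.250 | 0.173–0.174 | 71–73% | 86% |

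In the first row the pooled model falsely declares mediation in 91–93% of trials (single-level) or 36–38% (workshop-level). With slopes 0 / 0.2 the single-level figure is 34–36%. With the interaction included, single-level coverage of the ACT value is 93–94% in all three rows.

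**4. Missing a real pathway** (single-level, pooled versus ACT-specific detection).

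- Slopes 0.4 / 0: 84% versus 97%. The slope is halved but usually still detected.
- Slopes 0.2 / 0: 34% versus 66%.
- Slopes 0.4 / −0.4: 2% versus 97%.

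An outright miss therefore needs a weak ACT slope or opposing slopes.

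**5. Price of the interaction when slopes are equal.**

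- Single-level, slope 0.35: interval width 0.215 to 0.243 (0.243/0.215 = 1.13); power 0.96 to 0.95.
- Single-level, slope 0.2: interval about 25% wider; power 0.90 to 0.67.
- Workshop-level, slope 0.35: width 0.351 to 0.475 (0.475/0.351 = 1.35); power about 0.67 to 0.43 (0.63 to 0.36 in a second run).

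**6. Testing the interaction.** In the single-level model, power is about 42% for a slope difference of 0.2 and 92–93% for 0.4. A non-significant test would not establish equal slopes.

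**The case against.** The strongest reply has five parts.

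- *The plan is silent; it does not impose a constraint.* A reader might infer that the model fixes one common slope. The documents give no equations and no equality constraint, and a two-level model may separate within- from between-workshop slopes. This stands. What can be said is that no slope is arm-specific.
- *Single-level figures are not properties of the planned model.* A reader might infer that false mediation would be declared in nine of ten trials. On the workshop-level path the figure is about 36%, and coverage of the ACT value is about 64%, not 7–9%. This stands for the error rates. The bias in the point estimate remains in both.
- *Unequal slopes are speculative.* The AC workshop also covers how depressive and anxiety symptoms shape pain, and ACT-trained therapists lead both workshops. No slope data are given. This stands: the documents do not show that ACT loosens the link in its arm alone.
- *The aim may simply mean benefit attributable to ACT.* That reading fits the other aims, which compare ACT with AC. It is tenable, but the text does not settle it, so the plan should.
- *The remedy is expensive.* A reader might conclude that the ACT-arm estimate should replace the pooled one. Section 5 of the working shows why not: with equal slopes the loss of power can be large. This stands, and it shapes the fix.

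**Conclusion.** The concern holds in limited form. Aim B is worded for ACT recipients, the planned indirect effect is an ACT-versus-AC quantity, and the two agree only if the mediator-to-outcome slopes are equal in the two arms. The plan neither states nor checks that assumption.

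If the slopes differ, the bias for the ACT pathway is about a·(b0 − b1)/2, for equal arms and similar mediator variance. It is 0.125 in the 0 / 0.5 example and nil when slopes are equal. How often it would produce a wrong declaration depends on assumed path sizes and on which level of the model carries the effect. Neither stand-in is the full multilevel model.

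The documents do not support saying that the pooled analysis is wrong in itself, or that the slopes do differ. This is a secondary aim described as exploring a pathway, and no primary conclusion depends on it. It is a cheap improvement that should be settled before the data are analysed, because a later choice of model would be post hoc.

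**What to change.** In the mediation paragraph of the Data Analysis section:

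1. Keep the pooled ACT-versus-AC indirect effect, and state that it describes the pathway under ACT only if there is no intervention-by-mediator interaction.
2. Pre-specify a companion model for each mediator and outcome with an intervention-by-mediator term. From it report the ACT-arm indirect effect (effect on the mediator times the ACT slope), both arm slopes, and the interaction with its confidence interval.
3. Report both models whatever the interaction test shows, and do not use that test to choose between them.
4. Base any statement about the pathway in ACT recipients on the ACT-arm estimate, and any statement about the ACT-versus-AC indirect effect on the pooled one.

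The cost is plan wording and analysis work, with no new data. The downside is the lower precision of the ACT-arm estimate. With equal slopes, intervals are about 13–25% wider in the single-level model and 33–35% wider on the workshop-level path, with the power losses shown in the working. The plan should acknowledge this, so that an imprecise ACT-arm result is not read as absence of mediation.

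### Secondary aim B regresses outcome change on a mediator change that shares its baseline and lies inside its window, with no baseline-adjusted or lagged-outcome model beside it

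*Combined protocol and SAP*

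**What the plan says.** Under Data Analysis, the paragraph on secondary aim (B) sets out to explore a causal pathway from arm to outcome. The outcome is "the dependent variable Y (changes in pain & function) measured at the subject level within clusters"; the same paragraph gives its span as baseline to 6 months. The mediators are falls in distress and gains in coping, taken "from baseline to 6 weeks, and baseline to 3 months as mediators". The variables listed are arm, mediator changes and outcome changes. As to estimation, "multilevel structural equation modeling (MSEM) will be used to estimate and test the direct and indirect effects to assess multilevel mediation", and the design is called 2-1-1 with workshops as clusters. The Secondary Aims under Objectives give the same definitions: mediator changes "from baseline to 6 weeks and 3 months will be used as potential mediators for changes in pain and functioning at 6 months".

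Neither place names a baseline mediator, a baseline outcome, an earlier postoperative outcome or a mediator-outcome confounder. The general covariate rule in Data Analysis takes effect only "if any demographic, baseline, time from workshop to surgery, or perioperative variables" differ between the arms, and it is written for estimating group mean differences.

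**The concern.** Workshops are randomised to arm, but nobody is randomised to a level of distress or acceptance. The mediator-to-outcome path is therefore observational, and its slope can be non-zero without any mediator effect in two ways.

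- **Shared baseline.** Both changes subtract the same baseline visit. If mediator and outcome are correlated there and each drifts back towards its mean, the two changes move together.
- **Shared early interval.** Pain or function change before 6 weeks or 3 months is part of the outcome change, and may itself move distress or acceptance at that visit.

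The covariate rule answers neither, because this confounding needs no imbalance between arms. A false slope combined with a real ACT effect on the mediator, which secondary aim A looks for, would appear as an indirect effect. The trial could then attribute benefit to a mechanism that did not operate.

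**Working it through.** The plan gives no power or error rate for the mediation analysis, so there is no planned figure to reproduce.

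**Inputs from Sample Size:** 300 analysable participants, 6 per workshop on average (300/6 = 50 workshops), ICC 0.06.

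**Assumed, because the documents are silent:** ACT moves the mediator by 0.5 SD; baseline mediator-outcome correlation r of 0.3 to 0.5; baseline-to-follow-up stability s of 0.3 to 0.7; unit variances. The true mediator effect is set to 0.

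**1. Slope of outcome change on mediator change.** With M0, Y0 at baseline and Mt, Y6 at follow-up:

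slope = [cov(Mt,Y6) − cov(Mt,Y0) − cov(M0,Y6) + cov(M0,Y0)] / [2(1−s)]

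- Separate autoregressions with independent innovations: the numerator is r(1−s)², so the slope is r(1−s)/2. The range is 0.3×0.3/2 = 0.045 to 0.5×0.7/2 = 0.175, or about 0.05 to 0.18. At r = s = 0.5 it is 0.125.
- Stable-trait correlation: all four covariances equal r, so the slope is 0.

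**2. How often mediation is declared under separate autoregressions.** This is the joint test of both paths at 0.05. The pooled fit is subject-level regression with workshop-robust errors. The two-level fit is a maximum-likelihood model testing the between-workshop path, shown without and with baseline clustering of 0.06 (600 simulated trials per setting).

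| r | s | Slope by formula | Pooled | Two-level |
|---|---|---|---|---|
| 0.3 | 0.7 | 0.045 | 13% | 5.5% / 4.0% |
| 0.5 | 0.5 | 0.125 | 53% | 4.5% / 5.5% |
| 0.5 | 0.3 | 0.175 | 78% | 2.0% / 5.7% |

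Using observed workshop means instead gave 5% to 18%. In a separate pooled run (2,000 trials, r = 0.4, s = 0.5) the rate was 41%. It fell to 2% when ACT did not move the mediator.

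**3. The baseline-adjusted model.** Under separate autoregressions its pooled slope is 0.00 and its false-mediation rate 4% to 6%. Under a stable trait with cross-correlation 0.3 and stability 0.5, regress Y6 on Mt, M0 and Y0. By symmetry Mt and M0 share a coefficient b; let c be the coefficient of Y0.

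- 1.5b + 0.3c = 0.3
- 0.6b + c = 0.5

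Substituting c = 0.5 − 0.6b gives 1.32b = 0.15, so b = 0.114. The change model gives 0 here. In pooled simulation the adjusted model declared mediation in 44% to 53% of trials.

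**4. Influences after baseline (pooled fits only).** Let the 3-month mediator and 6-month outcome have residual correlation q, with r = 0.4 and s = 0.5. The change slope is 0.10 + q(1−s²)/[2(1−s)] = 0.10 + 0.75q, and the baseline-adjusted slope is q.

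| q | Change: slope (simulated), rate | Baseline-adjusted: slope (simulated), rate |
|---|---|---|
| 0.1 | 0.173, 80% | 0.099, 39% |
| 0.2 | 0.250, 96% | 0.200, 92% |
| 0.3 | 0.326, 97% | 0.301, 99% |

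If pain instead drives 3-month distress with a concurrent effect of 0.15, the false slope is 0.21 (change), 0.12 (baseline-adjusted) and 0.07 (also adjusted for the 6-week outcome).

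**5. Arm-to-mediator path.** Adding the baseline mediator multiplies the standard error by √[(1−s²)/(2(1−s))] = √[(1+s)/2]. At s = 0.5 this is 0.866, a 13% reduction. Simulation gave 11% to 13%.

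**The case against.** The strongest reply is that the plan does not specify a pooled regression. In a 2-1-1 design arm varies only between workshops, and a multilevel structural equation model separates that level from the person level, where most of the shared-baseline artefact sits. This stands: the two-level rates above are near nominal. It has limits. A near-nominal rejection rate with about 50 workshops partly reflects low precision, the post-baseline case in step 4 was not run in a two-level model, and a fit that does not separate the levels would behave like the pooled one.

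Second, change scores remove stable confounding that baseline adjustment removes only partly. This also stands, by step 3. The separate-autoregression process further implies that the mediator-outcome correlation falls from 0.5 to 0.5×0.5×0.5 = 0.125 at follow-up when r = s = 0.5, and nothing in the documents supports that.

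Third, the mediators are measured before the 6-month endpoint. That is true, and endpoint order is respected, but the outcome change still contains the interval over which the mediator change accrues. This applies to 6 weeks as well as 3 months.

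A reader might infer that the trial would report false mediation in some 12% to 78% of cases, or that baseline adjustment is a replacement without a downside. The documents support neither. The first rests on assumed correlations and a pooled fit, and the second fails under a stable trait. Eligibility based on pain and distress may also shrink their correlation in the sample: under illustrative cut-offs, population values of 0.3 to 0.5 fell to about −0.05 to 0.15, with pooled false rates of 5% to 10%.

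**Conclusion.** The concern holds as a gap in specification and interpretation. The only mediation model planned is change on change, with overlapping windows and nothing to address mediator-outcome confounding or early pain change acting on the mediator. The size and direction of any bias cannot be fixed from the documents. In a level-conflated fit the false slope ranges from 0 (stable trait) to about 0.05 to 0.18 (separate autoregressions), and was larger in the pooled runs with post-baseline influences. A two-level test of the between-workshop path holds its error rate near nominal against the shared-baseline artefact; against early pain change it is untested here. Aim B is secondary and described as exploring a pathway. The primary efficacy tests are untouched.

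**What to change.** Amend the secondary aim (B) paragraph:

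1. Include the baseline mediator as a covariate in the arm-to-mediator equation, to gain precision.
2. Keep the change-score model and pre-specify beside it a model of the 6-month outcome on arm and follow-up mediator, with baseline mediator and baseline outcome as covariates. For the 3-month mediator, add the 6-week outcome.
3. Claim mediation only if the models agree; otherwise describe the result as associational. State the no-confounding assumption in either case, because step 4 shows that both models can be wrong in the same direction.
4. State which level's mediator-to-outcome slope enters the indirect effect, since the error rate turns on it.

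The pre-randomization assessment and the 6-week, 3-month and 6-month surveys already collect BPI, KOOS, DASS-21, CPAQ and CPVI, so no new data are needed. The cost is a little more analysis and a more guarded conclusion where the models disagree. The 6-week outcome cannot remove pain change between 6 weeks and 3 months, so some ambiguity remains.
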